6.2.5.2. Sensitivity/Supplementary Analysis

Sensitivity Analyses

In order to assess the sensitivity of the dose Bayesian Emax dose-response model to the location and informativeness of the prior distributions, sensitivity analyses may be performed that will utilize alternative prior distributions.

6.3. Other Endpoint(s)

6.3.1. Proportion of participants achieving improvement in fibrosis by ≥1 stage independent of changes in NAS, based on assessment by sponsor-identified central pathologist(s), at Week 48 compared to baseline

6.3.1.1. Main Analysis

- Estimand strategy: Composite (Section 2.1.2).
- Analysis set: Evaluable (Section 4). All randomized participants who take at least 1 dose
 of investigational product who have provided evaluable baseline data for the endpoint
 (i.e. baseline biopsy data).
- Analysis methodology: For assessing dose response, the proportion of responders at Week 48 will be analyzed using a Bayesian Emax dose-response model. For assessing pairwise comparisons, the proportion of responders at Week 48 will be analyzed an using logistic regression models with treatment and baseline fibrosis stage (F2/F3) as factors (Section 5.2.1).
- Intercurrent events and missing data: If a participant discontinues treatment or from the study due to lack of efficacy or toleration prior to Week 48 or if they do not have evaluable Week 48 Biopsy data, they will be considered to be a non-responder. If they withdraw from treatment for other reasons (not related to lack of efficacy or toleration) and have evaluable biopsy data at withdrawal or Week 48, these data will be utilized to determine whether they are a responder or not.
- The number and proportion of responders for this tertiary endpoint at Week 48 will be presented for each treatment arm.
- The model-estimated proportion of responders (and 90% credible interval) for each treatment arm, and the placebo-adjusted proportion of responders for BID each dose (and 90% credible interval), and odds ratio and risk difference (and corresponding 90% confidence interval) for other treatment comparisons will be presented at Week 48. For comparisons of DGAT2i+ACCi BID doses vs corresponding DGAT2i BID monotherapy doses corresponding 50% confidence interval will also be provided.
- 6.3.2. Proportion of participants achieving resolution of NASH without worsening of fibrosis and improvement in fibrosis by ≥1 stage without worsening of NASH, based on assessment by sponsor-identified central pathologist(s), at Week 48 compared to baseline

6.3.2.1. Main Analysis

- Estimand strategy: Composite (Section 2.1.2).
- Analysis set: Evaluable (Section 4). All randomized participants who take at least 1 dose
 of investigational product who have provided evaluable baseline data for the endpoint
 (i.e. baseline biopsy data).

- Analysis methodology: For assessing dose response, the proportion of responders at Week 48 will be analyzed using a Bayesian Emax dose-response model. For assessing pairwise comparisons, the proportion of responders at Week 48 will be analyzed an using logistic regression models with treatment and baseline fibrosis stage (F2/F3) as factors (Section 5.2.1).
- Intercurrent events and missing data: If a participant discontinues treatment or from the study due to lack of efficacy or toleration prior to Week 48 or if they do not have evaluable Week 48 Biopsy data, they will be considered to be a non-responder. If they withdraw from treatment for other reasons (not related to lack of efficacy or toleration) and have evaluable biopsy data at withdrawal or Week 48, these data will be utilized to determine whether they are a responder or not.
- The number and proportion of responders for this tertiary endpoint at Week 48 will be presented for each treatment arm.
- The model-estimated proportion of responders (and 90% credible interval) for each treatment arm, and the placebo-adjusted proportion of responders for BID each dose (and 90% credible interval), and odds ratio and risk difference (and corresponding 90% confidence interval) for other treatment comparisons will be presented at Week 48. For comparisons of DGAT2i+ACCi BID doses vs corresponding DGAT2i BID monotherapy doses corresponding 50% confidence interval will also be provided.

6.3.3. Proportion of participants with progression of fibrosis by ≥1 stage (defined as an increase of at least 1 stage in the Brunt-Kleiner scale compared to baseline) independent of changes in NAS, at Week 48

6.3.3.1. Main Analysis

- Estimand strategy: Composite (Section 2.1.3).
- Analysis set: Evaluable (Section 4). All randomized participants who take at least 1 dose
 of investigational product who have provided evaluable baseline data for the endpoint
 (i.e. baseline biopsy data).
- Analysis methodology: For assessing dose response, the proportion of responders at
 Week 48 (defined as the proportion of participants with worsening of fibrosis by ≥1 stage
 on liver biopsy, as assessed by sponsor identified central pathologist(s), at Week 48) will
 be analyzed using a Bayesian Emax dose-response model. For assessing pairwise
 comparisons, the proportion of responders at Week 48 will be analyzed using logistic
 regression models with treatment and baseline fibrosis stage (F2/F3) as factors
 (Section 5.2.1).
- Intercurrent events and missing data: If a participant discontinues treatment or from the study due to lack of efficacy or toleration prior to Week 48 or if they do not have evaluable Week 48 biopsy data, they will be considered to be a responder (as this assumes that these participants will also have worsened). If a participant has improved or

maintained the same level of fibrosis compared to baseline, then that participant will be termed as a non-responder.

- If they withdraw from treatment for other reasons (not related to lack of efficacy or toleration) and have evaluable data at withdrawal or Week 48, these data will be utilized to determine whether they are a responder or not.
- The number and proportion of responders for this endpoint at Week 48 will be presented
 for each treatment arm. The model-estimated proportion of responders (and 90% credible
 interval) for each treatment arm, and the placebo-adjusted proportion of responders for
 BID each dose (and 90% credible interval), and odds ratio and risk difference (and
 corresponding 90% confidence interval) for other treatment comparisons will be
 presented at Week 48. For comparisons of DGAT2i+ACCi BID doses vs corresponding
 DGAT2i BID monotherapy doses corresponding 50% confidence interval will also be
 provided.

6.3.4. Proportion of participants with progression of fibrosis by ≥1 stage and worsening of ≥2 points in Total NAS at Week 48

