 Estimand 3.1: Using a composite estimand strategy, in patients with biopsy-confirmed NASH and fibrosis, on eligibility assessment of SCR2 biopsy as assessed by the sponsoridentified central pathologist(s), estimate the treatment effect of DGAT2i doses administered alone and coadministration of DGAT2i + ACCi relative to placebo, and coadministration of DGAT2i + ACCi, relative to DGAT2i alone, in terms of the proportion of 'clinical responders' (for the purposes of analysis), defined as participants with worsening in liver biopsy endpoint components at Week 48 and treating all cases of withdrawal from treatment for lack of efficacy or toleration also as 'responders'. Participants who withdraw from treatment for other reasons but have evaluable biopsy data at withdrawal or at Week 48 will have their biopsy data assessed to determine whether they are 'responders' or not. Participants with no Week 48 biopsy data will be considered to be 'responders'. Participants who improve or remain the same compared to baseline in their liver biopsy endpoint components are treated as 'non-responders', as response for these endpoints is defined as a worsening in liver biopsy endpoint components. All treatment effect contrasts will be obtained through fitting the Bayesian dose-response and/or exposure-response models with a logit transformation, or logistic regression models.

Finally, exploratory estimands to assess endpoints related to additional definitions of 'clinical response' are defined as follows:

• Estimand 3.2: Using a composite estimand strategy, in patients with biopsy-confirmed NASH and fibrosis, on eligibility assessment of SCR2 biopsy as assessed by the sponsor-identified central pathologist(s), estimate the treatment effect of DGAT2i doses administered alone and coadministration of DGAT2i + ACCi relative to placebo, and coadministration of DGAT2i + ACCi, relative to DGAT2i alone, in terms of the proportion of 'clinical responders', defined as participants achieving improvement in fibrosis by ≥1 stage independent of changes in NAS, at Week 48 and treating all cases of withdrawal from treatment for lack of efficacy or toleration as non-responders.

[figure not shown]

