2.2. Study Design

The detailed set-up of the study is summarized below -

Figure 1. Study Design

This is a multicenter, multinational, randomized, double-blind, double-dummy, placebo-controlled, parallel-group, evaluation of DGAT2i alone, and DGAT2i+ACCi. Approximately 350 participants (50 per arm) with biopsy confirmed NASH with F2-F3 fibrosis, as assessed by sponsor-identified central pathologist(s), will be randomly assigned to the study intervention to ensure approximately 280 evaluable participants (40 per arm) offer evaluable data for the primary objective.

Participants will be randomized in a balanced ratio, using a computer-generated randomization code, to receive either double-blind, double-dummy placebo, 1 of 4 doses/dosing regimens of DGAT2i alone, or 1 of 2 dose-levels of DGAT2i+ACCi for a treatment duration of up to 48-weeks.

For participants randomized before Protocol Amendment 1 is enacted, those randomized to either of the 2 QD (DGAT2i 150 mg QD and DGAT2i 300 mg QD) dosing regimens of DGAT2i alone will remain in the study but will be switched to the corresponding BID dosing regimen of DGAT2i alone, maintaining the assigned total daily dose and the double-blind, double-dummy design. New randomization to the QD treatment arms will cease, after Health Authority (where applicable) and IRB/EC approvals of Protocol Amendment 1. Therefore, following Protocol Amendment 1, participants will be randomized to one of the following treatment arms:

Placebo

DGAT2i (Ervogastat) BID dose arms (for characterization of dose-response):

- DGAT2i 25 mg BID, total daily dose of 50 mg
- DGAT2i 75 mg BID, total daily dose of 150 mg
- DGAT2i 150 mg BID, total daily dose of 300 mg
- DGAT2i 300 mg BID, total daily dose of 600 mg

DGAT2i (Ervogastat) + ACCi (Clesacostat) coadministration dose arms:

- DGAT2i 150 mg BID + ACCi 5 mg BID
- DGAT2i 300 mg BID + ACCi 10 mg BID

The treatment group labels in programmed outputs will be as follows:

Placebo	PF-5571	PF-5571	PF-5571	PF-5571	PF-5571	PF-5571	Tota1
	25 mg	75 mg	150 mg	150 mg	300 mg	300 mg	
	BID	BID	BID	BID+	BID	BID+	
				PF1304 5		PF1304 10	
				mg BID		mg BID	

Following footnote to be included on all tables: PF5571 = Ervogastat and PF1304 = Clesacostat Note: A 'Total' column is required when summarizing baseline of population randomized

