3.3. Other Endpoint(s)

- Proportion of participants achieving improvement in fibrosis by ≥1 stage independent of changes in NAS, based on assessment by sponsor-identified central pathologist(s), at Week 48 compared to baseline
- Proportion of participants achieving resolution of NASH without worsening of fibrosis
 and improvement in fibrosis by ≥1 stage without worsening of NASH, based on
 assessment by sponsor-identified central pathologist(s), at Week 48 compared to baseline

- Proportion of participants with worsening in liver biopsy endpoint components based on assessment by sponsor-identified central pathologist(s) at Week 48:
 - Progression of fibrosis by ≥1 stage (defined as an increase of at least 1 stage in the Brunt-Kleiner scale compared to baseline) independent of changes in NAS
 - Progression of fibrosis by ≥1 stage and worsening of ≥2 points in Total NAS
 - Worsening of ≥2 points in Total NAS (defined as an increase of at least 2 points in Total NAS compared to baseline) independent of changes in fibrosis

Other tertiary/exploratory endpoints are as shown below. The analyses of these endpoints are assessed for efficacy up to Week 48, but the analyses of blood based biomarkers will also include data up to and including Week 50 to allow an assessment of off-treatment effects::

- Percent change in liver fat (assessed via MRI-PDFF in Imaging substudy population), over time up to Week 48
- Percent change in liver volume (assessed via Magnetic resonance imaging (MRI) in Imaging substudy population), over time up to Week 48
- Percent change in CCI (assessed via MRI in Imaging substudy population), over time up to Week 48
- Percent change in CCI (assessed via MRI in Imaging substudy population), over time up to Week 48
- Percent change from baseline in liver fat as assessed via Controlled attenuation parameter (CAPTM) measure by FibroScan[®], (entire study population), over time up to Week 48
- Percent change from baseline in liver stiffness (assessed via Vibration-Controlled Transient Elastography (VCTE™) using FibroScan® (entire study population)), over time up to Week 48
- Percent change from baseline in Liver Function Tests Alanine aminotransferase (ALT), Aspartate aminotransferase (AST), Alkaline phosphatase (ALP), Gamma-glutamyl transferase (GGT), Total Bilirubin, Direct Bilirubin, and Total Bile Acids over time up to Week 50

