CFB-Wk48/DC = nonevaluable (for NAS or fibrosis component(s) required for endpoint)	 If case did not complete IPV → count as non-responder If case completed IPV, utilize Week 48-IPV results for whichever component(s) is/are nonevaluable as Week 48 result in CFB (ie, IPV consensus results if available); if only parallel is available, select results from pathologist that had highest NAS score and/or fibrosis stage Qualitative assessment will only include data from whichever component is evaluable, if any (either NAS components or fibrosis)

Observed cases (including any alternative cases utilized for analysis as described above) will be used when analyzing variables using an MMRM.

For the analysis of safety endpoints, the sponsor data standard rules for imputation will be applied.

PK Concentrations below the limit of quantification

 In all data presentations (except listings), concentrations below the limit of quantification (BLQ) will be set to zero. In listings BLQ values will be reported as "<LLQ", where LLQ will be replaced with the value for the lower limit of quantification.

Deviations, missing concentrations, and anomalous values for PK

In summary tables, statistics will be calculated having set concentrations to missing if one of the following cases is true:

- A concentration has been collected as ND (ie not done) or NS (ie no sample),
- A deviation in visit window is of sufficient concern or a concentration has been flagged anomalous by the pharmacokineticist.

Note that summary statistics will not be presented at a particular visit if more than 50% of the PK data are missing.

Efficacy and Pharmacodynamic (PD) endpoints

- Missing data for all efficacy and PD endpoints will be treated as such and no imputed values will be derived when presenting descriptive statistics at scheduled assessments.
- Concentrations below Lower Limit of Quantification (LLQ) will be set to half-LLQ (ie LLQ/2) for summary outputs; in listings BLQ values will be reported as "<LLQ".
- Derived data by calculation (eg indirect bilirubin) will not follow the rule described above and will be reported as <LLQ (in listings) with a derived value of (<negative value> minus 0.0001 = positive value) when generating summary statistics, as required.
- Any values above the Upper Limit of Quantification (ULQ) will be assigned to the ULQ for display purposes in figures and for computation of summary statistics; in listings ULQ values will be reported as ">ULQ".

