- For Fibroscan® Baseline derivation, the last evaluable measurement from SCR1 to Day 1 pre-dose can be used (i.e. closest results obtained prior to dosing on Day 1 (Visit 5)).
- Patient Reported Outcomes: All PRO endpoints will be analyzed according to the analysis windows above (and the Week 36 analysis window will only be used for the PROs completed at Week 36). Note that only the daily assessments recorded in the e-Diary prior to dosing on Day 1 [Visit 5] will be included in the derivation of Baseline NASH Symptom Diary scores. Any daily assessments captured in the e-Diary on Day 1 or later will be excluded from the Baseline scores. For PGI-S, as this is recorded twice at each visit, the records will be selected based on the below method:

Closest to Target (first) – Selects the record closest to the target. If two records are equi-distant from the target (before and after), select the 1st record.

- For the following assessments, the above visit windows will not be used:
 - Liver Biopsy:

For liver biopsy assessments, any pre-randomization biopsy data will be considered to be 'Baseline', and any post-randomization biopsy data collected on or after the Week 24 visit will be considered to be 'Week 48/End of Study'. This is so that any liver biopsies performed at the 'early termination' visit, which will be an unplanned visit (after Week 24), can be windowed appropriately so that data will be summarized and included in the analysis as required.

 MRI: All MRI endpoints will be analyzed according to the nominal visit to which they relate.

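### The only modelled analysis of the three exploratory worsening endpoints scores missing biopsies and efficacy or toleration stops as histological worsening; add a modelled analysis of the biopsies actually read

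*SAP*

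**What the plan says.** SAP Section 3.3 lists three worsening endpoints. The first is "Progression of fibrosis by ≥1 stage (defined as an increase of at least 1 stage in the Brunt-Kleiner scale compared to baseline"), regardless of NAS. The second is that progression together with a Total NAS rise of at least 2 points. The third is the NAS rise alone.

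Section 6.3.3.1 sets the rule: "If a participant discontinues treatment or from the study due to lack of efficacy or toleration prior to Week 48", or if evaluable Week 48 biopsy data are lacking, "they will be considered to be a responder (as this assumes that these participants will also have worsened". Sections 6.3.4.1 and 6.3.5.1 repeat it. Estimand 3.1 in Section 2.1.3 agrees: "Participants with no Week 48 biopsy data will be considered to be 'responders". So do Table 8 and Appendix 1. The resulting binary variable goes into the Bayesian Emax model and the logistic regressions.

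Two provisions limit or contradict the rule:

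- Appendix 2.1 narrows what counts as missing: "any post-randomization biopsy data collected on or after the Week 24 visit will be considered to be 'Week 48/End of Study".
- Table 10 in Section 5.3 deals with a non-evaluable Week 48 read that has no intra-pathologist-variability (IPV) re-read: "If case did not complete IPV → count as non-responder". For a worsening endpoint, that means not worsened. The opening of Section 5.3 also imputes non-response for composite estimands, with no exception for these endpoints.

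Appendix 1 lists an observed-data summary for each worsening endpoint. Unlike for the primary and secondary endpoints, it lists no sensitivity analysis. Section 6.1.1.2 adds shift tables with a category for missing Week 48 results.

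**The concern.** Scoring missing as failure works differently for a harm than for a benefit. For a response endpoint it removes possible successes and dilutes the rate. For an infrequent harm it adds events, and these may outnumber the ones seen on biopsy. The modelled estimates then depend heavily on who lacked a usable second biopsy or stopped treatment, and less on histology.

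Unequal stopping between arms is foreseeable. Protocol Section 7.1 names thresholds for adverse reactions identified with ACCi among the reasons for stopping, and only the two combination arms receive ACCi. If such stops are classed as toleration, they count as liver worsening in the arms being compared with placebo and with monotherapy.

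The rule also reaches beyond missing data. Protocol Sections 7.1 and 8.1.1 allow a participant to stop treatment, stay in the study and have a Week 48 biopsy. Someone who stopped for toleration and whose biopsy improved is scored as worsened by one sentence of SAP Section 6.3.3.1 and as not worsened by the next.

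**Working it through.** **Inputs.** SAP Section 2.2 gives "Approximately 350 participants (50 per arm) with biopsy confirmed NASH with F2-F3 fibrosis", "randomly assigned to the study intervention to ensure approximately 280 evaluable participants (40 per arm) offer evaluable data for the primary objective". The worsening rate on read biopsies, *w*, is not in the documents; it is assumed to lie between 2% and 40%. Missing shares by arm are not given either; the unequal values below are illustrations.

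**Implied missing share.** 1 − 280/350 = 20%. Checked in reverse, 280/0.80 = 350 and 40/0.80 = 50, so the plan's figures reproduce. The 20% is inferred, because the plan does not state a missing-biopsy rate.

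**Share of events that are imputed.** With missing share *m*, the composite rate is *m* + (1 − *m*)*w*, and the imputed share is *m*/[*m* + (1 − *m*)*w*]. At *m* = 20%, 10 of 50 participants per arm are imputed events:

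| *w* | Observed events (of 40) | Composite rate (of 50) | Imputed share |
|---|---|---|---|
| 2% | 0.8 | 21.6% | 93% |
| 5% | 2 | 24% | 83% |
| 10% | 4 | 28% | 71% |
| 15% | 6 | 32% | 62.5% |
| 20% | 8 | 36% | 56% |
| 25% | 10 | 40% | 50% |
| 30% | 12 | 44% | 45% |
| 40% | 16 | 52% | 38% |

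The break-even is *w* = *m*/(1 − *m*): 11% at 10% missing, 25% at 20% and 43% at 30%. The joint endpoint needs both kinds of worsening, so its true rate cannot exceed that of either component, and its imputed share is at least as high. Efficacy or toleration stops who do have a biopsy would add further non-histological events.

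**Equal missingness (20% in both arms).** The difference becomes (1 − *m*)(*w*₀ − *w*₁), which is 0.8 times the truth. For a true 20% against 10%, the composite gives 0.20 + 0.80 × 0.20 = 36% against 0.20 + 0.80 × 0.10 = 28%. That is 8 points instead of 10, and the odds ratio moves from 0.44 to 0.69. The approximate chance that a 90% interval excludes zero is 22% with 50 per arm under the composite, against 35% with 40 per arm on read biopsies.

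**Unequal missingness, equal *w*.** The false difference is (*m*₁ − *m*₀)(1 − *w*). For 15% against 25% missing at *w* = 10%:

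- 0.15 + 0.85 × 0.10 = 23.5%
- 0.25 + 0.75 × 0.10 = 32.5%

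This is 9 points of false excess. It is 9.5 points at *w* = 5% and 8 points at *w* = 20%. With 50 per arm, the 90% interval would exclude zero on the harm side about 26% of the time at *w* = 10%, against a nominal 5%.

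**Unequal missingness hiding a benefit.** Suppose worsening is truly halved, from 20% to 10%, with 15% and 25% missing. The rates become 0.15 + 0.85 × 0.20 = 32.0% and 0.25 + 0.75 × 0.10 = 32.5%, so the benefit disappears.

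**Impossible events.** Protocol Section 5.1 admits Total NAS from 4 to 8, and SAP Section 3.2 sets the maximum at 8. From a baseline of 7 or 8 a rise of 2 points cannot occur, yet a missing biopsy is scored as one.

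**Conflicting direction.** If all 20% were coded as non-response under the opening of Section 5.3, the rate at *w* = 10% would be 0.80 × 0.10 = 8%. Under Section 6.3.3.1 it is 28%.

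**The case against.** The strongest reply is that this is a deliberate estimand and not a slip. Estimand 3.1 has its own definition, its own row in Table 8 and its own entries in Appendix 1, and the SAP states its assumption openly. A composite strategy is meant to count tolerability failure as a bad outcome. The endpoints are exploratory, with no hypothesis tests. Observed-data summaries and shift tables let a reader separate read worsening from imputed worsening, and counting biopsies from Week 24 onward reduces missingness. A model on read biopsies alone would also be sparse.

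Most of this stands, and it is why the composite should not be replaced. It does not answer the narrower point. The planned safeguards are descriptive, and no modelled dose response or contrast estimates histological worsening itself.

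A reader might also infer three stronger things that the documents do not support:

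- *Most events will be missing data.* At 20% missing this requires worsening below 25%, and no worsening rate is given.
- *The models merely compare dropout.* A false contrast needs missingness to differ between arms. Equal missingness only dilutes the effect.
- *Every missing biopsy is scored as worsening.* Appendix 2.1 rescues biopsies from Week 24 onward, and Table 10 scores some non-evaluable reads the opposite way.

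**Conclusion.** The point holds as a low-severity request. At the implied 20%, imputed events make up from 93% (*w* = 2%) to 38% (*w* = 40%) of the total, and half or more when *w* is 25% or lower. A gap in missingness between arms shifts the contrast by (1 − *w*) points for each point of gap. Depending on the direction of that gap, the composite can suggest harm that is absent or hide a benefit.

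These sizes rest on reading 280 of 350 as the share with a usable Week 48 biopsy, and on assumed worsening rates and arm-level gaps. The documents do not show that dropout will differ by arm; they only make it foreseeable. The conflict between Section 5.3 and Sections 6.3.3.1 to 6.3.5.1 needs no assumption, since the text would let a programmer code these endpoints in either direction.

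**What to change.** Keep Estimand 3.1 and make three changes to the SAP:

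1. For each worsening endpoint, pre-specify a modelled supplementary analysis in participants with evaluable paired reads. Include Week 48 biopsies taken off treatment, and assume missing at random given treatment and baseline fibrosis stage. The Estimand 1.2 data rule cannot be reused unchanged, because it censors data collected after treatment withdrawal.
2. Report it beside the composite result, with the number of imputed and observed events in each arm.
3. Reconcile the opening of Section 5.3 and Table 10 with Sections 6.3.3.1 to 6.3.5.1, so that the direction of imputation for worsening endpoints is stated once.

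The cost is SAP wording and mostly reused model code. The added analysis depends on missing at random and has few events: about 2 per arm at 5% worsening with 40 evaluable (40 × 0.05). The Emax fit may be unstable and the pairwise estimates will be imprecise.
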